7.2. Special Situations

In addition to adverse events, the following categories of data are considered to be 'special situations' and also require reporting to Global Medical Safety (GMS), whereby processing and reporting are determined in accordance with national reporting requirements for each marketed product in a particular country or territory:

- Drug exposure during pregnancy (maternal and paternal)
- Exposure to a Janssen medicinal product from breastfeeding
- Overdose of a Janssen medicinal product
- Suspected abuse/misuse of a Janssen medicinal product
- Inadvertent or accidental exposure to a Janssen medicinal product (e.g., occupational exposure)
- Any failure of expected pharmacological action (i.e., lack of effect) of a Janssen medicinal product
- Medication error involving a Janssen medicinal product (with or without patient exposure to the Janssen medicinal product, e.g., name confusion)
- Suspected transmission of any infectious agent via administration of a Janssen medicinal product
- Unexpected therapeutic or clinical benefit from use of a Janssen medicinal product
- Off-label use of a Janssen medicinal product

7.3. Study Completion/Termination**7.3.1. Study Completion**

The study will be completed three years after registry start. Interim analyses will be conducted to check the number of BDQ-treated patients captured in the registry. Updates on patient accrual and timelines for study completion will be provided annually as part of the Interim Report. A descriptive report on patient counts and the safety profile with respect to study objectives will be prepared in alignment with the PSUR schedule.

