1.1.5. Mortality and Morbidity

MDR-TB represents a major threat to global TB control. On average, these patients require a treatment duration of 2 years on average with the substantially more toxic and less potent second-line anti-TB drugs. Cure rates are lower and mortality higher than for DS TB, particularly if patients are coinfecting with HIV. According to the latest WHO data, only 48% of the MDR-TB patients in the 2010 cohort of detected cases were successfully treated, reflecting high mortality rates and loss to follow-up (WHO 2013²⁷).

Mortality and case fatality estimates are uncertain partly due to incomplete coverage of global drug resistance surveillance and the lack of direct measurements of MDR-TB deaths. An estimated 170,000 (range 102,000 to 242,000) deaths caused by MDR-TB occurred in 2012, including those with HIV infection (WHO 2013²⁷). This high overall mortality reflects poor diagnostic and treatment capacity for MDR-TB globally. Even for patients that make it into good treatment programmes, overall mortality still exceeds 10%, with a range of 8% to 21% (Wells 2010²⁴). Two independently conducted meta-analyses from 2009, each including approximately 30 studies in MDR-TB, found death as a reported outcome in 11% of treated patients (Johnston 2009¹⁷, Orenstein 2009²²). A more recent meta-analysis reflecting data from 9,153 individual patients reported a mortality rate of 15% (95% CI: 14.5% to 16%). Patients who died were significantly older, more likely to be HIV co-infected, with more extensive disease (defined as acid fast bacilli [AFB]-smear positive or cavities on chest x-ray if no information about AFB-smear), and/or had prior therapy (Ahuja 2012¹).

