2. OVERVIEW OF STUDY DESIGN

2.1. Study Design

The research design uses a prospective observational comparative cohort study of patients treated for MDR-TB in multiple countries included in the early adopter (WHO pilot) program. A case of tuberculosis is one in which a health worker (clinician or other medical practitioner) has diagnosed TB. MDR-TB is defined as TB caused by *Mycobacterium tuberculosis* resistant in vitro to the effects of isoniazid and rifampicin, with or without resistance to any other drugs. Patients are enrolled in the registry by their healthcare provider once the healthcare provider diagnoses a patient with MDR-TB (inception cohort for comparison) or decides to treat with BDQ (exposure cohort specifically identifying indication for use for BDQ). All patient follow-up data will be collected at each visit from the healthcare provider during the course of BDQ treatment and for an additional 24 months after the last BDQ dose unless the patient is lost to follow-up or has died. Similar follow-up will be conducted for MDR-TB patients not treated with BDQ. Two options are under evaluation for the recruitment of MDR-TB patients not treated with BDQ. The first option under consideration is to include patients who are eligible for BDQ, but refuse BDQ at sites where BDQ is available. The second

option under consideration is the use of a stepwise cluster wedge design to enroll patients at centers who would be eligible for BDQ, but do not have access. The method for selecting MDR-TB patients not treated with BDQ will depend on how BDQ is made available in the early adopter countries. All patients newly diagnosed and treated for MDR-TB will be eligible for inclusion in the registry. Additionally, all patients initiating BDQ treatment will be eligible for inclusion in the registry regardless of the indication for use. All patients meeting the inclusion criteria and providing informed consent for participation in the study will be enrolled. The registry enrollment period will be open for 36 months with an additional 24 months of follow-up for safety assessment. This enrollment period should allow the enrollment of approximately 3000 MDR-TB patients treated with BDQ.

Data will be collected in an observational manner such that the management of the patient is determined by the patient and the caregiver and not influenced by the registry protocol. The registry will describe care as it is provided.

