4. STATISTICAL METHODS

4.1. Sample Size and Study Precision

The three year enrollment period of the registry is estimated to result in an enrollment of 3000 to 5000 BDQ-treated patients.

A cohort of 3000 patients gives a 95% probability of identifying an adverse event with an incidence rate of 1:1000.

Based on the sample size estimates below, a registry of 1000 BDQ-exposed patients would have 95% power to detect a Relative Risk of 2 assuming $\alpha = 0.05$ and a 1:1 ratio of BDQ-exposed patients to unexposed patients for events that occur with a frequency of at least 3%.

Power and Sample Size for Adverse Events Occurring with a Frequency of at Least 3%							
Exposed	Relative Risk						
	1.5	2	3	4	5	7	10
0	0.049985	0.049985	0.049985	0.049985	0.049985	0.049985	0.049985
100	0.133214	0.252768	0.559428	0.828643	0.961157	0.999754	1.000000
200	0.190756	0.414883	0.844041	0.986772	0.999721	1.000000	1.000000
300	0.243884	0.552078	0.952777	0.999299	0.999999	1.000000	1.000000
400	0.294233	0.663681	0.987120	0.999970	1.000000	1.000000	1.000000
500	0.342210	0.751574	0.996745	0.999999	1.000000	1.000000	1.000000
600	0.387925	0.819043	0.999224	1.000000	1.000000	1.000000	1.000000
700	0.431400	0.869774	0.999824	1.000000	1.000000	1.000000	1.000000
800	0.472639	0.907271	0.999961	1.000000	1.000000	1.000000	1.000000
900	0.511649	0.934588	0.999992	1.000000	1.000000	1.000000	1.000000
1,000	0.548449	0.954244	0.999998	1.000000	1.000000	1.000000	1.000000

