4.2.2. Outcome Definitions and Measures

The registry is designed to observe several aspects of MDR-TB treatment such as drug utilization characteristics, treatment outcomes (clinical and microbiologic), and safety outcomes (adverse events and mortality). All study outcomes will be documented by the healthcare provider and will be reported up to 24 months after discontinuation of MDR-TB treatment.

Study outcome definitions will include:

- Medical indication for BDQ treatment as reported by the healthcare provider
- Frequency of use of expert medical consultation in MDR-TB treatment with BDQ
- Drug susceptibility of MDR-TB isolates (Pre-XDR, XDR) and drug susceptibility to BDQ based on MIC reported

-
- Laboratory location and type performing susceptibility testing as well as type of test performed
 - Past treatment history, past medical history, prior medications utilization, and health care site of treatment
 - Use of DOT for drug administration
 - Adverse events including deaths over the course of MDR-TB therapy recorded using WHO guidance for pharmacovigilance of medicines used in the treatment of tuberculosis (WHO 2012²⁵)
 - Comorbidities prior to initiating MDR-TB therapy as well as over the course of therapy
 - Concomitant medications prior to initiating MDR-TB therapy as well as over the course of therapy
 - Reason for discontinuation of MDR-TB therapy
 - Change in TB background regimen (Y/N)
 - Cavities on chest x-ray
 - Acid fast bacilli-smear $\geq 1+$ (Y/N)

The following definitions will be used for treatment outcomes among MDR-TB cases (WHO, 2013³⁰):

- Cured: Treatment completed as recommended by the national policy without evidence of failure AND three or more consecutive cultures taken at least 30 days apart are negative after the intensive phase^a.
- Treatment Completed: Treatment completed as recommended by the national policy without evidence of failure BUT no record that three or more consecutive cultures taken at least 30 days apart are negative after the intensive phase^a.
- Treatment Failed: Treatment terminated or need for permanent regimen change of at least two anti-TB drugs because of:
 - Lack of conversion^b by the end of the intensive phase^a, *or*
 - Bacteriological reversion^b in the continuation phase after conversion^b to negative, *or*

-
- Evidence of additional acquired resistance to fluoroquinolones or second-line injectable drugs, *or*
 - Adverse drug reactions (ADRs).

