4.2.4. Length of Follow-up

Each patient will be followed for 24 months from the discontinuation of MDR-TB therapy, until death, or loss to follow-up within the cohort, whichever occurs first. Time varying variables will be recorded at each patient visit.

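### Section 7.3.1 completes the study at month 36, when enrollment closes, although Section 2.1 plans 24 further months of follow-up; the end date and the follow-up anchor must be reconciled

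*Protocol*

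**What the plan says.** The protocol describes the length of the study in several places.

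- **Section 7.3.1** (Study Completion): "The study will be completed three years after registry start". The same paragraph promises annual updates on accrual and on the completion timeline.
- **Section 2.1**, repeated in the Synopsis: "The registry enrollment period will be open for 36 months with an additional 24 months of follow-up for safety assessment".
- **Section 4.1** confirms the enrollment window: "The three year enrollment period of the registry is estimated to result in an enrollment of 3000 to 5000 BDQ-treated patients".

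The rule for individual patients also has two versions.

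- **Section 2.1** and the Synopsis collect data during BDQ treatment and "for an additional 24 months after the last BDQ dose unless the patient is lost to follow-up or has died", with similar follow-up for patients not given BDQ.
- **Section 4.2.4**: "Each patient will be followed for 24 months from the discontinuation of MDR-TB therapy", ending earlier only on death or loss to follow-up. **Section 4.2.2** agrees that outcomes "will be reported up to 24 months after discontinuation of MDR-TB treatment".

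On treatment length, **Section 1.1.5** says that "these patients require a treatment duration of 2 years on average". Section 1.1.4 describes treatment of up to two years.

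**The concern.** Month 36 is the last month of enrollment. If the study is complete on that date, none of the 24 months that Section 2.1 adds can take place, and a patient enrolled at the end contributes no observation.

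The primary objectives in Section 1.3.1 include comparing treatment outcomes between BDQ-treated and other patients, and estimating the relative risk of death. Under Section 4.2.2, cured and treatment completed both require that treatment has been completed, and treatment success is their sum. These outcomes, together with safety and mortality after treatment, are what an end at month 36 would cut off.

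A second difficulty remains once the date is corrected. Follow-up runs from the last BDQ dose in one place and from the end of all MDR-TB therapy in another. The two can fall at different times, and the first has no direct counterpart in patients who never receive BDQ.

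**Working it through.** **Inputs**

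- Enrollment: 36 months (Synopsis, 2.1, 4.1).
- Added follow-up: 24 months (Synopsis, 2.1).
- Post-therapy follow-up per patient: 24 months (4.2.2, 4.2.4).
- Therapy duration T: 24 months, the average in 1.1.5. Values of 12, 18 and 20 months are assumptions to show the range.
- Accrual: uniform over 36 months, with therapy starting at enrollment. Both are assumptions.

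**Can the stated three years be reproduced?** No.

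- 24 months after enrollment closes: 36 + 24 = 60 months.
- 24 months after the last BDQ dose, for a patient enrolled at month 36: 36 + BDQ duration + 24, which is at least 60 months.
- 24 months after the end of therapy, same patient: 36 + 24 + 24 = 84 months, or 36 + 18 + 24 = 78 with an assumed 18 months of therapy.

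**Share of patients who can reach a given point.** A patient enrolled at month e reaches a point t months later, before registry close C, if e ≤ C − t. Under uniform accrual the share is max(0, min(36, C − t)) / 36. Use t = T for the end of therapy and t = T + 24 for full post-therapy follow-up.

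| Close C | T (months) | Reach end of therapy | Have 24 months after therapy |
|---|---|---|---|
| 36 | 24 | 12/36 = 33% | max(0, −12)/36 = 0% |
| 36 | 20 | 16/36 = 44% | 0% |
| 36 | 18 | 18/36 = 50% | 0% |
| 36 | 12 | 24/36 = 67% | 0% |
| 60 | 24 | 36/36 = 100% | 12/36 = 33% |
| 60 | 20 | 100% | 16/36 = 44% |
| 60 | 18 | 100% | 18/36 = 50% |

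Mean potential observation is 36 − 18 = 18 months with a close at month 36, and 60 − 18 = 42 months with a close at month 60.

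**Counting from the last BDQ dose instead.** With a close at month 36, even a BDQ course of zero length allows only (36 − 24)/36 = 33% to complete 24 months. With an assumed 6-month course it is (36 − 30)/36 = 17%. With a close at month 60 and the same 6 months it is (60 − 30)/36 = 83%.

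**Outcomes that do not wait for the end of therapy.** Under the MDR-TB definitions in 4.2.2, failure can be assigned for lack of conversion by the end of the intensive phase (8 months is proposed where no maximum is set) or for adverse drug reactions. By month 36, (36 − 8)/36 = 78% of patients could have reached 8 months. Under the definitions for other cases, failure applies from month 5. Death and loss to follow-up can occur at any time during treatment.

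**The case against.** The strongest reply is that 7.3.1 contains a drafting slip. The 36 + 24 plan is stated twice, two other sections require follow-up after therapy, and the paragraph itself expects the timeline to be updated each year. On that reading nobody means to close at month 36. This is plausible, and the documents do not show that an early close is intended. It does not remove the contradiction: 7.3.1 is the only section that defines completion, it refers to the study and not to enrollment, and updating a timeline does not reconcile it with another one.

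A reader might infer that most patients would end as not evaluated. That is not shown. The 33% counts only those who could reach month 24; it leaves out patients already classified as failed, died or lost. Those groups may be large, since Section 1.1.5 reports that only 48% of a 2010 MDR-TB cohort were treated successfully. Even the statement that most patients could not finish therapy needs a duration above 18 months under uniform accrual. It is also wrong to place failure with the outcomes fixed at the end of treatment.

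The inputs are rough. Two years is an average, while 1.1.4 gives it as an upper limit; anyone treated longer would miss even the 100% shown for month 60. BDQ patients enter when the decision to give BDQ is made, possibly after MDR-TB therapy began, so some would finish sooner than the table assumes. These points move the percentages and leave the calendar conflict as it is.

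Finally, Section 4.4.2.2 already plans person-time rates and Poisson regression for adverse events, including death. For those analyses an early close means lost follow-up, not miscounted events.

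**Conclusion.** The point holds as an internal contradiction with a material consequence. Completion at three years cannot coexist with 36 months of enrollment plus 24 months of follow-up, and no follow-up rule in the protocol gives 36 months.

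If 7.3.1 were applied, no patient could have 24 months of observation after a therapy of 12 months or more. That result does not depend on the accrual pattern, because 12 + 24 = 36. The share able to finish therapy, 33% at two years and 44–50% at 18–20 months, rests on uniform accrual and on therapy starting at enrollment; slower early accrual would lower it. The damage is concentrated in cured, treatment completed, treatment success, and safety and mortality after treatment. It does not extend equally to every outcome.

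Moving to 60 months settles the conflict with Section 2.1's registry timeline but not with 4.2.4. With two-year therapy, only about 33% of patients would then have the full 24 months after therapy. The two follow-up anchors also remain unreconciled until the text chooses one.

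**What to change.** 1. **Section 7.3.1:** replace the completion sentence with completion at 60 months from registry start (36 months of enrollment plus 24 months of follow-up), matching the Synopsis and 2.1. This is a wording change and adds no time beyond the stated design.
2. **Follow-up anchor:** use one starting point for the 24 months in the Synopsis, 2.1, 4.2.2 and 4.2.4, defined so that it applies to both cohorts.
3. **Section 4.2.4:** choose between two forms. Either follow-up is up to 24 months with administrative censoring at registry close, which costs only wording and accepts that many patients will have less than 24 months after therapy; or completion is the date on which the last patient reaches 24 months, about month 84 with two-year therapy, which is 84 − 60 = 24 months longer than Section 2.1 plans.
4. **Treatment-outcome proportions (4.4.2.1):** restrict them to patients whose enrollment date leaves enough potential follow-up before the close, or use a method that handles censoring. The restriction should depend on enrollment date and not on whether treatment was seen to finish. No change of method is needed for adverse events and death, which 4.4.2.2 already analyses by person-time.

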7.3.2. Study Termination

JRD has the right to close study sites, e.g. in case of non-compliance with protocol, IRB guidelines, Sponsor procedures and ICH guidelines.

